Phase I is a one week baseline phase without treatment to quantify baseline pre-treatment measures (see Figure 1). In **Phase II**, subjects will be randomized to 1 of 4 treatment conditions for 8 weeks: 1) active light treatment using a fluorescent light box (10,000 lux white light for 30 minutes daily) plus a placebo pill, 2) placebo inactive negative ion generator (30 minutes daily) with fluoxetine 20 mg/d, 3) placebo inactive negative ion generator (30 minutes daily) plus placebo pill (double placebo), or 4) combined active light treatment using a fluorescent light box (10,000

lux white light for 30 minutes daily) plus fluoxetine 20 mg/d. Randomization will be conducted centrally via a web-based computerized system and stratified by sex and centre.

Figure 1. Protocol Summary (also see Appendix 1 – Summary of Procedures)

The primary measure of efficacy will be change score (baseline to termination) on the Montgomery-Asberg Depression Rating Scale (MADRS). Secondary measures of efficacy will include clinical response (50% or greater improvement in MADRS scores) and remission (final MADRS score of 10 or less), scores on the 24-item Hamilton Depression Rating Scale (Ham-24), the CGI, the Quick Inventory of Depressive Symptoms (QIDS-SR, Rush 2003), the Lam Employment Absence and Productivity Scale, and the Quality of Life, Enjoyment and Satisfaction Questionnaire. All of these outcome measures are widely used in depression research studies, are sensitive to change, and have been well validated (e.g., Lam et al, 2005). Safety and adverse events data will also be systematically recorded and compared across conditions. Utilization of health services data will be captured to estimate cost-effectiveness of each active treatment condition compared to placebo.

C. Outcome Measures (see Appendix 1)

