5. Any retinal disease or systemic illness with active retinal involvement (e.g. diabetes) that precludes the use of bright light.
6. Patients who have a history of severe allergies and multiple drug adverse reactions.
7. Regular or current use of other psychotropic drugs including lithium and tryptophan.
8. Patients treated with beta blocking drugs.
9. Hypertensive patients being treated with guanethidine, reserpine, clonidine or methyldopa (because of possible mood-altering effects of those drugs).
10. Use of monoamine oxidase inhibitors within 14 days of Visit 1 (to ensure no drug interactions between fluoxetine and MAOIs), or use of heterocyclic antidepressant within 7 days of Visit 1 (to ensure adequate washout period of two weeks between stopping previous drug and start of treatment at Visit 2).
11. Previous use of fluoxetine or light therapy.
12. Treatment resistance in the current episode, as defined by failure (lack of clinically significant response) of two or more antidepressants given at therapeutic doses for at least 6 weeks.
13. Patients who started formal psychotherapy (e.g. cognitive-behavioural or interpersonal psychotherapy) within 3 months of Visit 1, or who plan to initiate such psychotherapy during this study.
14. Patients involved in any other form of treatment for depression.

Sample Size

Based on a power analysis using a minimal clinically important difference (MCID) and data derived from the largest and highest quality study of light and medication treatment for MDD (Martiny et al, 2005), we propose a sample size of 216 patients overall, or at least 54 randomized to each of the 4 groups with allowance for a 20% dropout rate (the average in our previous studies), recruited over 3 years. With regard to the primary hypothesis, this sample size will allow us to detect a difference of 3.5 points on the MADRS (widely regarded as a MCID in depression

treatment studies) between conditions with 80% power at two-sided testing at a Bonferroni-corrected $\alpha=0.017$ (3 planned comparisons: fluoxetine vs. placebo, light vs. placebo, light+fluoxetine vs. placebo).

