For the secondary hypotheses, a sample size of 216 patients will allow us to detect a risk difference in response or remission rates of 15% between conditions. It also allows us to detect a minimal difference between means of at least 5 points on scale scores such as quality of life measures, based on an anticipated pooled standard deviation of 8 points (based on previous studies, e.g., Michalak et al, 2005), at 80% power and an alpha of 0.05 on two-sided testing. Again, these differences are considered clinically meaningful and are similar to the effect sizes seen in meta-analyses of antidepressant drugs vs. placebo.

E. Treatments

Treatment Device Method

The active treatment consists of a fluorescent (4000 Kelvin broad spectrum) light box that emits 10,000 lux ($2600 \mu\text{w}/\text{cm}^2$) white light measured by digital photometer at the level of the cornea when subjects are positioned at 18 inches from the screen. The light box will be fitted with a screen that filters out wavelengths below 400 nm (ultraviolet wavelengths).

Subjects will be given standardized instructions on how to use the light box (supplied by Uplift Technologies, Canada). In summary, subjects will be instructed about properly positioning themselves and the light box to maintain the correct distance to the light source. A measuring cord attached to the light box will be used to ensure that the distance is properly maintained. They will be instructed to stay awake with their eyes open during light exposure, but they will not be required to look directly at the light source, i.e., they can read or eat during the light treatment. The instructions will be repeated at each clinic visit. Subjects will take home the light box and sit under the light box for 30 minutes, within 15 minutes of arising from habitual wake time.

The placebo control treatment consists of a negative ion generator (SphereOne Inc.) modified to emit an audible hum, but which is deactivated so no negative ions are emitted. This credible placebo condition has been used in previous studies by our group and others (Desan et al, 2007; Eastman et al, 1998; Goel et al, 2005).

The same instructions as used for the light box will be used for the ion generator. Patients will be instructed to use the ion generator for 30 minutes, within 15 minutes of arising from habitual wake time.

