During the protocol, specific measures will be taken to maintain the blind for subjects. Subjects will be instructed not to talk about their treatment device. Subjects will not be scheduled for appointments at the clinic at the same time, so they will not be able to talk among themselves. Research personnel will minimize time with the subject and will not discuss the treatments with them.

Data Management

Data will be managed and analyzed by the Verity Strategy Group Inc. This group has extensive experience in managing large datasets and procedures in place to ensure integrity and

verification of data handling and analysis. They will design the web-Case Report Form (CRF) as a web-based dataform on a secure web site, for direct data entry by research staff.

J. Early Terminations

Every effort will be made to keep the subject in the study for the duration of the study. Acceptable reasons for premature discontinuation include the following:

1. Request of subject.
2. Decision of the investigator.
3. Serious adverse events.
4. Protocol variance (e.g. non-compliance).

K. Data Analysis

All randomized subjects who receive treatment will be included in the analysis based on intent-to-treat, defined as randomized subjects who have at least one follow up rating. Ineligible subjects who are inappropriately randomized will be excluded from the analysis. Eligibility will be reviewed by the independent adjudication committee (chaired by [name]) blind to assigned treatment and response.

For the analyses the treatment variables will remain coded and the analysts and investigators will remain blinded to variable identity during analysis and interpretation.

The change from baseline to Week 8 (or termination) in the MADRS is the primary endpoint. In order to preserve comparability with previous depression treatments studies, a similar method of analysis will be used. Missing data will be imputed using last observation carried forward (LOCF). An ANOVA on the change scores will be conducted using preplanned pairwise contrasts.

The secondary outcomes will also be analyzed using a similar ANOVA analysis, when appropriate. Categorical data (such as proportions of the sample with adverse events) will be analyzed using binary logistic regression with preplanned pairwise contrasts, chi-square tests and Fisher's exact test where cell sizes warrant.

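### The claim that 216 patients can detect a 15-point difference in response or remission is wrong: for control rates of 20–50%, power is about 34–41% at 54 per arm and the detectable difference is about 25–30 points

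*Protocol*

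**What the plan says.** Section D of the protocol (Sample Size) sets the trial's size with the words "we propose a sample size of 216 patients overall", split as "at least 54 randomized to each of the 4 groups with allowance for a 20% dropout rate". The number is justified by the primary MADRS comparison. For the secondary hypotheses the text then adds that "a sample size of 216 patients will allow us to detect a risk difference in response or remission rates of 15% between conditions". That sentence gives no control rate, alpha or power of its own. The next sentence carries the statement on to scale scores: a difference of 5 points, "based on an anticipated pooled standard deviation of 8 points", "at 80% power and an alpha of 0.05 on two-sided testing". A closing sentence describes these differences as clinically meaningful and in line with antidepressant meta-analyses.

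Section B defines response as at least 50% improvement on the MADRS and remission as a final MADRS of at most 10, and names them first among the secondary efficacy measures. Section K says that categorical data are analysed by "binary logistic regression with preplanned pairwise contrasts", alongside chi-square and Fisher's exact tests. The analysis set there is "defined as randomized subjects who have at least one follow up rating".

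**The concern.** The 15-point claim is attached to the total of 216, but no planned comparison of conditions uses 216 patients. Each contrast sets one arm of 54 against another. With so few per arm, a 15-point difference between two proportions is far below what can be detected with 80% power unless the rates lie close to 0 or 100%.

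Response and remission are the results that clinicians read most easily. Anyone assessing the protocol, an ethics board for instance, is told that the trial can detect a clinically meaningful difference on them. For control rates of 20–50%, a real 15-point benefit would be missed roughly three times in five to two times in three at 54 per arm. A non-significant result could then be taken as evidence against a meaningful benefit on the strength of this sentence.

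**Working it through.** **Inputs**
- Per arm: 216 / 4 = 54 randomised; 54 × 0.8 = 43.2, so about 43 after dropout (Section D). The analysis set in Section K needs only one follow-up rating, so the analysed number lies between 43 and 54; 54 is the favourable bound.
- Comparison: pairwise between arms (Section K).
- Alpha 0.05 two-sided and power 80% (Section D, the sentence on scale scores, read as covering the paragraph).
- Control rate: not given. Assumption: 20–50%, with 1–84% scanned.

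**Step 1. Reproduce the companion figure, to confirm the basis**

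n per arm = 2 (SD/δ)² (z₀.₉₇₅ + z₀.₈₀)² = 2 × (8/5)² × (1.960 + 0.842)² ≈ 40.2, so 41, or 41/0.8 = 51.25, so 52 with dropout. Power for 5 points is Φ(5 / (8√(2/n)) − 1.960):
- n = 43: Φ(2.898 − 1.960) = 0.83
- n = 54: Φ(3.248 − 1.960) = 0.90

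The 5-point claim is therefore correct on a pairwise, two-sided 0.05 basis.

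**Step 2. Apply the same basis to the 15-point claim**

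With p̄ = (p₁ + p₂)/2 and no continuity correction:

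power = Φ( [ |p₂ − p₁| √n − 1.960 √(2p̄(1 − p̄)) ] / √(p₁(1 − p₁) + p₂(1 − p₂)) )

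Worked case, 30% vs 45%, n = 54:
- 0.15 × √54 = 1.102
- 1.960 × √(2 × 0.375 × 0.625) = 1.342
- √(0.2100 + 0.2475) = 0.676
- power = Φ((1.102 − 1.342)/0.676) = Φ(−0.354) = 0.36

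The number needed is n = [1.342 + 0.842 × 0.676]² / 0.15² = 1.911² / 0.0225 ≈ 162.3, so 163 per arm.

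| Control vs active | Power, 54/arm | Power, 43/arm | Detectable at 80%, 54/arm | Detectable at 80%, 43/arm | n/arm for 15 points |
|---|---|---|---|---|---|
| 20 vs 35% | 0.41 | 0.34 | 25.0 | 28.3 | 138 |
| 30 vs 45% | 0.36 | 0.30 | 26.4 | 29.6 | 163 |
| 35 vs 50% | 0.35 | 0.29 | 26.7 | 29.8 | 170 |
| 40 vs 55% | 0.34 | 0.28 | 26.6 | 29.7 | 173 |
| 50 vs 65% | 0.35 | 0.29 | 25.8 | 28.6 | 170 |

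The requirement peaks at 174 per arm, for a control rate of 42.5%. Allowing for 20% dropout, 138–174 evaluable becomes 138/0.8 to 174/0.8, about 173–218 randomised per arm.

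**Step 3. Look for any reading that yields 15 points**
- Other control rates, 54 per arm: 15 vs 30% gives 0.46, 10 vs 25% gives 0.54, 5 vs 20% gives 0.66 and 2 vs 17% gives 0.77. Power reaches 0.81 only at 1 vs 16% and its mirror, 84 vs 99%.
- For control rates of 20–50%:
  - one-sided 0.05, 54 per arm: 0.47–0.54
  - alpha 0.05/3, 54 per arm: 0.20–0.26
  - one arm against the other three (54 vs 162): 0.48–0.54
  - pooled halves, 108 vs 108: 0.60–0.70
  - pooled halves after dropout, 86 vs 86: 0.50–0.60

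**The case against.** The arithmetic is hard to contest, but five points can be made on the other side.

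- **Secondary outcomes only.** The sentence does not determine the sample size, which rests on the MADRS comparison. That is true. Correcting it changes no patient number, endpoint or test, and this limits the consequence, but the figure remains false.
- **The control rate is the reviewer's assumption, and response and remission need not share one.** This stands for the exact numbers. If placebo remission were 5–15%, power at 54 per arm would be 0.46–0.66, not 0.34–0.41. That is still below 80%.
- **The 80% power and 0.05 belong grammatically to the next sentence.** That is so. But that sentence is worded as a continuation of the same claim, no other level is offered, and its own figure reproduces on that basis.
- **Pooled factorial margins may have been meant.** At 108 vs 108, 10 vs 25% does give 0.83. After dropout (86 vs 86) it falls to 0.74, and Section K specifies pairwise contrasts, so this reading does not save the claim.
- **The misreading of a null result is a prediction.** It is; nothing in the protocol plans such an inference. The case for correction rests on the wrong number itself.

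**Conclusion.** The 15-point claim is wrong as written. For assumed control rates of 20–50% and two-sided 0.05, pairwise power for 15 points is 34–41% at 54 per arm and 28–34% at 43. The detectable difference at 80% power is 25.0–26.7 and 28.3–29.8 points respectively. The plan has about a third of the patients per arm that 15 points would require. The exact figures depend on the control rate, which the protocol does not give. The conclusion does not: at 54 per arm it holds for any control rate from about 2% to 83%. The companion claim on scale scores is sound, and the primary sample size is untouched.

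**What to change.** In Section D (Sample Size), replace the 15% sentence with one that names the assumed control rate, the number per arm, alpha and power. For example:

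> Assuming a control rate between 20% and 50%, 54 (43) patients per arm give 80% power at two-sided 0.05 to detect a pairwise difference in response or remission of about 25–27 (28–30) percentage points; power for a 15-point difference is about 34–41% (28–34%).

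If the investigators have separate expected placebo rates for response and remission, they should state each and recompute from it. The closing sentence, which calls the stated differences clinically meaningful and similar to meta-analytic effects, must be reread, since it was written with 15 points in mind. Presenting the two rates mainly as estimates with confidence intervals would suit this precision, but is optional and separate from the correction.

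The cost is one replaced sentence and a check of one other. No patients are added and the analysis does not change; the stated sensitivity simply becomes less favourable.

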3. QIDS-SR
4. Adverse Events Scale
5. Health Economic Assessment
6. LEAPS (Visits 2, 5 and 7 only)
7. QLESQ (Visits 2, 5, and 7 only)
8. MEQ (Visits 2, 5, and 7 only)
9. Weight (Visits 2, 5, and 7 only)
10. FSS (Every 2 weeks)
11. PSQI (Visits 2, 5, and 7 only)

Patients will be encouraged to contact the investigator or a member of the research staff at any time between visits concerning adverse events or worsening of symptoms. Adverse Events will be classified as mild, moderate or severe. These are defined according to widely used criteria in antidepressant clinical trials as follows:

1. Mild event - noted change in patient condition that does not affect activity.
2. Moderate event - mild disruption in usual activity.
3. Severe - major disruption in usual activity. The investigator shall promptly report all adverse events to the Study Coordinator by prompt submission of the web-CRF. **IF THE ADVERSE EVENT IS ALARMING, IT SHALL BE REPORTED TO THE STUDY COORDINATOR IMMEDIATELY BY TELEPHONE.** Serious events requiring immediate notification by telephone to the Study Coordinator are those events which:
 - a) Result in death
 - b) Are life threatening
 - c) Are severely or permanently disabling
 - d) Require inpatient hospitalization or prolongation of an existing hospital stay
 - e) Result in an incidence of cancer
 - f) Result from a drug overdose or reaction after drug withdrawal.

The following compliance parameters will be collected/reviewed at Visit 2 through Visit 7.

1. Daily logs of time spent using treatment device
2. Capsule counts from medication blister packs.

G. Concomitant Therapy

Drugs which may be taken by the subject include any prescription or over-the-counter medication not specifically excluded in the protocol. These may include aspirin, birth control pills, vitamins, etc.

Drugs that must **NOT** be taken by the subject during the course of the study include: sympathomimetics; CNS depressants; narcotics; monoamine oxidase inhibitors; antidepressants; amino acids (including tryptophan and tyrosine); hypnotics; modafinil; melatonin or melatonin agonists; beta blocking drugs; other psychotropic drugs including lithium, psychostimulants (e.g.,

d-amphetamine, methylphenidate), antipsychotics and benzodiazepines, and herbaceuticals (e.g., St. John's wort). Patients requiring excluded concomitant drugs will be discontinued from the study.

H. Data Safety Monitoring Committee

An independent physician and biostatistician not involved in the trial will comprise the Data Safety Monitoring Committee (DSMC). Although we do not anticipate serious adverse events, the DSMC will monitor all adverse events reports. They will have access to the randomization codes, if necessary, to determine if a particular condition is associated with serious adverse events.

I. Quality Assurance

Compliance Monitoring

Methods for quality assurance will be strictly observed. A start-up videoconference involving the study site personnel (principal investigators, co-investigators, and research assistants) and the Study Coordinator will be held prior to commencing the study. During this meeting, great care will be taken to fully explain the study procedures and web-CRF completion.

Inter-rater reliability for the MADRS/Ham-24 will be established and confirmed for the telephone raters using taped interviews. Previous studies by the co-investigators have established the reliability of these outcome measures.

Each year throughout the study, the Study Coordinator will regularly visit each site to ensure that accurate and complete data are collected and properly recorded. At least 25% of all records will be randomly selected and the web-CRF will be manually audited against original charts and documents.

The web-CRF will be constructed to collect the data required by the protocol (see Data Management section). All data and information requested on the web-CRF must be completed by the investigator and/or their research staff, including results of clinical examinations. Completion of each web-CRF will be verified weekly by the Study Coordinator.

Concealment of Allocation and Maintenance of Blinded Assignment

There will be a central computerized randomization process, stratified for site and randomized in random blocks of 4 or 8. Concealment of allocation will be accomplished using a computerized web-based system that reveals the treatment allocation only after the subject is assigned a unique subject number. Site-specific randomization codes will be kept at each site, with 24-hour availability in the (very unlikely) event that the blind needs to be broken for urgent medical reasons.

During the protocol, specific measures will be taken to maintain the blind for subjects. Subjects will be instructed not to talk about their treatment device. Subjects will not be scheduled for appointments at the clinic at the same time, so they will not be able to talk among themselves. Research personnel will minimize time with the subject and will not discuss the treatments with them.

Data Management

Data will be managed and analyzed by the Verity Strategy Group Inc. This group has extensive experience in managing large datasets and procedures in place to ensure integrity and

verification of data handling and analysis. They will design the web-Case Report Form (CRF) as a web-based dataform on a secure web site, for direct data entry by research staff.

J. Early Terminations

Every effort will be made to keep the subject in the study for the duration of the study. Acceptable reasons for premature discontinuation include the following:

1. Request of subject.
2. Decision of the investigator.
3. Serious adverse events.
4. Protocol variance (e.g. non-compliance).

K. Data Analysis

All randomized subjects who receive treatment will be included in the analysis based on intent-to-treat, defined as randomized subjects who have at least one follow up rating. Ineligible subjects who are inappropriately randomized will be excluded from the analysis. Eligibility will be reviewed by the independent adjudication committee (chaired by [name]) blind to assigned treatment and response.

For the analyses the treatment variables will remain coded and the analysts and investigators will remain blinded to variable identity during analysis and interpretation.

The change from baseline to Week 8 (or termination) in the MADRS is the primary endpoint. In order to preserve comparability with previous depression treatments studies, a similar method of analysis will be used. Missing data will be imputed using last observation carried forward (LOCF). An ANOVA on the change scores will be conducted using preplanned pairwise contrasts.

The secondary outcomes will also be analyzed using a similar ANOVA analysis, when appropriate. Categorical data (such as proportions of the sample with adverse events) will be analyzed using binary logistic regression with preplanned pairwise contrasts, chi-square tests and Fisher's exact test where cell sizes warrant.

A secondary confirmatory analysis will also be conducted using a mixed-effects model with repeated measures (MMRM), under the missing at random framework (Gueorguieva and Krystal, 2004). The baseline MADRS score will be used as a covariate under this model. This model will include treatment condition and visit factors as class fixed effects and subject as random effect as well as two interaction terms between treatment condition by visit and covariate by visit, and subject as random. The treatment condition factor will have 4 levels (two monotherapies, one placebo condition, and one combination condition) and the visit factor will have 4 levels (each of the 4 treatment visits). This model using all available post-baseline evaluation in Phase II will provide the baseline adjusted least-squares means (LS-means) estimates at Week 8 by treatment condition, as well as the differences of these estimates versus placebo conditions, with their corresponding standard errors, degrees of freedom, t-test statistics and associated 95% confidence intervals. The t-test statistic at Week 8 will be used to determine the statistical significance of the primary efficacy comparisons of active versus placebo conditions.

L. Informed Consent and Ethical Considerations

The investigator will prepare a written Informed Consent Document (ICD). The subject will read the ICD and the investigator will answer any questions he/she may have. The subject must indicate willingness to participate in the study by signing the ICD. The document must also be signed by a witness and an investigator. A copy of the signed ICD will be submitted to the Study Coordinator.

This study will be conducted according to guidelines established by Good Clinical Practice (Food and Drug Administration, www.fda.gov/oc/gcp/regulations.html). The Institutional Review Boards (IRBs, or research ethics committees) of each participating site must approve the protocol and ICD. Each investigator will provide the Study Coordinator with evidence that their IRB has approved the study before subjects are entered at that site.

M. Publications and Communications

This trial will be registered at www.clinicaltrials.com and at the Cochrane Collaboration clinical trials registry in accordance with the policy from the International Committee of Medical Journal Editors (De Angelis et al, 2004). The results of this trial will be presented at scientific conferences and published, using the CONSORT guidelines, in a peer-reviewed scientific journal.

N. List of Trial Site Investigators

[name]/[name]
Vancouver, BC.

[name]
Winnipeg, MB.

[name]/[name]
Toronto, ON.

[name], MDCM
Montreal, QC

[name]
St. John, NB.

[name]
Calgary, AB

[name]
Calgary, AB

O. References

Please refer to Research Proposal, p.12 of the Research Module.

P. Appendix

Summary of Procedures

Item	Visit 1 Screen	Visit 2 Week 0	Visit 3 Week 1	Visit 4 Week 2	Visit 5 Week 4	Visit 6 Week 6	Visit 7 ^a Week 8
Physician: ICD signed	X						
Physician: MINI/C-CASA	X						
Physician: Eligibility	X						
Physician: Demographic info	X						
Physician: Ham-17	X	X					
Study Coordinator (SC): SPAQ*/ASRS*/RSQ*	X						
SC/Web: Expectation of Response*		X					
Telephone: MADRS+Ham-24		X	X	X	X	X	X
Physician: CGI (-S and -I)		X	X	X	X	X	X
SC: Health Economic Assessment		X	X	X	X	X	X
SC/Web: QIDS-SR*		X	X	X	X	X	X
SC/Web: Adverse Events Scale*		X	X	X	X	X	X
SC/Web: FSS*		X		X	X	X	X
SC/Web: LEAPS*		X			X		X
SC/Web: Q-LES-Q*		X			X		X
SC/Web: PSQI*		X			X		X
SC/Web: MEQ*		X			X		X
SC: Weight		X			X		X
SC: Height		X					
SC: Device/drug instructions		X	X	X	X	X	
SC: Handout/return device		X					X
Physician: Debrief							X

^a or Termination visit, if patient withdraws.

* patient-rated.

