CLINICAL TRIAL PROTOCOL

Light and Ion Treatment to Enhance⁺ Medication Efficacy in Depression

(The LITE+MED Trial)

A Randomized Controlled Trial of Light Treatment and Fluoxetine in Patients with Nonseasonal Major Depressive Disorder

Principal Co-Investigators:

[name], University of British Columbia
[name]
[contact], [contact], [contact]

[name], University of Toronto

[name], University of Toronto

[name], University of BC

[name], University of Manitoba

[name], University of Toronto

[name], University of Toronto

[name], Sunnybrook Health Sciences Centre

[name], MDCM, McGill University

[name], Dalhousie University

[name], University of Calgary

[name], University of Calgary

Revised Version Date: November 18, 2010

CLINICAL TRIAL PROTOCOL

Light and Ion Treatment to Enhance+ Medication Efficacy in Depression.

A Randomized Controlled Trial of Light Treatment and Fluoxetine in Patients with Nonseasonal Major Depressive Disorder.

i. Table of Contents

A. Objectives	2
B. Overall Study Design	2
C. Outcome Measures	3
D. Study Population	5
E. Treatments	7
F. Procedures and Methods	8
G. Concomitant Therapy	9
H. Data Safety Monitoring Committee ...	10
I. Quality Assurance	10
J. Early Termination	11
K. Data Analysis	11
L. Informed Consent and Ethics	11
M. Publications and Communications	12
N. List of Investigators	12
O. References	12
P. Appendix: Summary of Procedures...13	

A. Study Objectives

The **primary objectives** of this study are to test the hypotheses that, in patients with nonseasonal major depressive disorder (MDD) of at least moderate severity: 1) light treatment with a fluorescent light box (10,000 lux white light for 30 minutes daily) is more effective than a placebo control condition, and 2) combined light treatment and antidepressant medication (fluoxetine) is more effective than placebo and both monotherapies.

The **secondary objectives** of this study are to investigate the effects of bright light treatment and fluoxetine on clinical response and remission rates, adverse events, quality of life, work productivity, and health services utilization.

[figure not shown]
B. Overall Study Design (see Figure 1)

This trial has been designed as a multicentre, double-blind, placebo-controlled, randomized, parallel-design study. A total of 216 patients meeting entry criteria will be enrolled at 6 centres over a 3 year period.

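### Sections B and I give different randomisation strata, and the listed MMRM terms include neither centre nor sex; if these factors are prognostic, the tests are conservative and some power is lost

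*Protocol*

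**What the plan says.** **Randomisation.** Section B (Overall Study Design) names two stratification factors: "Randomization will be conducted centrally via a web-based computerized system and stratified by sex and centre". Section I (Quality Assurance, under Concealment of Allocation and Maintenance of Blinded Assignment) names one, and adds the block sizes: "There will be a central computerized randomization process, stratified for site and randomized in random blocks of 4 or 8". Sex is not mentioned there.

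**Size.** Section B: "A total of 216 patients meeting entry criteria will be enrolled at 6 centres over a 3 year period". Section D, Sample Size: "at least 54 randomized to each of the 4 groups with allowance for a 20% dropout rate".

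**Analysis (Section K).** The primary analysis has one sentence on its model: "An ANOVA on the change scores will be conducted using preplanned pairwise contrasts". The MMRM is described term by term: "This model will include treatment condition and visit factors as class fixed effects and subject as random effect", with treatment-by-visit and covariate-by-visit interactions, and "The baseline MADRS score will be used as a covariate under this model". Section K calls the MMRM secondary and confirmatory, but also has its Week 8 t-test decide the significance of the primary active-versus-placebo comparisons. Neither centre nor sex is named in either description.

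**The concern.** There are two linked problems.

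First, whoever programs the web system has two specifications. Section I is the operational text, with the block sizes, so it is the natural one to build from. A list built from it as worded would leave the balance of sex to chance, although Section B promises to control it. A list cannot be rebuilt once patients have been allocated from it.

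Second, stratified allocation makes the arms alike on the strata, which removes between-stratum variance from the treatment contrast. A model without those factors still counts that variance as error. If the factors are prognostic, the reported standard error exceeds the true one, the test rejects less often than its nominal level, and power is lost.

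**Working it through.** **1. Strata implied by each section** (216 patients, 6 centres)

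- Section B, sex and centre: 6 × 2 = 12 strata; 216/12 = 18 patients on average.
- Section I, site as worded: 6 strata; 216/6 = 36 on average.

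Blocks of 4 or 8 suit four equal arms under either scheme, so the block sizes do not show which was meant.

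**2. The plan's sample size, to set the scale**

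Section D plans for 3.5 MADRS points, 80% power and two-sided alpha 0.017 (0.05/3 = 0.0167). It gives no MADRS standard deviation. Assuming 5.0:

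- n per arm = 2 × (2.387 + 0.842)² × 5.0² / 3.5² = 42.6, so 43.
- With 20% dropout, 43/0.8 = 53.75, so 54; 4 × 54 = 216.

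This matches the plan's figure, so 5.0 is used below. The sample size itself does not depend on the present point.

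**3. Closed-form size of the mismatch**

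Let R² be the share of variance in MADRS change explained by the strata (assumed). With full balance on the strata:

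- SE overstatement = 1/√(1 − R²) − 1
- true alpha = 2 × [1 − Φ(2.387/√(1 − R²))]

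| R² | SE overstated by | True alpha at nominal 0.017 |
|---|---|---|
| 2% | 1.0% | 0.016 |
| 5% | 2.6% | 0.014 |
| 10% | 5.4% | 0.012 |

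These figures assume that allocation is restricted on every factor counted in R², which is the Section B scheme, and that balance is perfect.

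**4. Simulation with imperfect balance**

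Set-up: 216 patients, four arms, six sites of equal expected size, a 35/65 sex split, permuted blocks of 4 or 8, 20% random dropout, SD 5.0, alpha 0.017, and R² shared equally between site and sex. There were 4,000 runs with no effect and 2,000 at 3.5 points. The site sizes, sex split and R² are assumptions. The model is the change-score ANOVA, with treatment only or with site and sex added.

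Sex-by-centre stratification:

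| R² | Treatment-only model SE / empirical SE (no effect) | Type I error, treatment only | Adjusted model SE | Power: treatment only → adjusted |
|---|---|---|---|---|
| 0% | 1.077 / 1.086 | 0.021 | 1.082 | 81% → 81% |
| 5% | 1.076 / 1.047 (+2.8%) | 0.015 | 1.053 | 81% → 82% |
| 10% | 1.077 / 1.040 (+3.6%) | 0.011 | 1.026 | 80% → 84% |
| 20% | 1.078 / 0.988 (+9.1%) | 0.010 | 0.967 | 83% → 90% |

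Monte Carlo error is about 0.002 on the type I error and about 1% on the empirical SE (1/√(2 × 4000) = 1.1%), so the 0.021 in the first row is compatible with 0.017. In the 3.5-point runs, the overstatement at R² 5%, 10% and 20% was 1.078/1.079 (nil), 1.076/1.030 (4.5%) and 1.078/0.986 (9.3%).

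Site-only stratification, no-effect runs: 1.077/1.090 (nil) at 5%, 1.075/1.054 (2.0%) at 10% and 1.076/1.038 (3.7%) at 20%. Only the site share is then removed from the contrast.

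**The case against.** **Section I does not exclude sex.** It is silent on sex and could be a shortened restatement of Section B. That stands: a reader might infer that Section I stratifies by site alone, and the text does not say so. But it is the operational text and omits a factor that Section B requires, so the two must still be aligned.

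**The primary model may be completed in an analysis plan that is not shown.** This largely stands. The ANOVA has one sentence and no list of terms, so it cannot be said to exclude the strata. The MMRM is different: its terms are listed without them, and Section K has its Week 8 test decide the primary comparisons.

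**A reader might infer that the tests are invalid, or that the standard errors must be wrong.** The documents support neither. The mismatch arises only if centre or sex predicts MADRS change, and its direction is conservative.

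**Nothing shows that centres differ in response.** This also stands. The protocol gives no such figure, and blinded telephone raters with a structured guide and established inter-rater reliability limit one source of centre differences. For that reason R² is shown only as an assumed range. Stratifying by site alone would also be a valid design, with sex balanced in expectation.

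**Conclusion.** Two things are firm. Sections B and I do not state the same strata and would give different lists (12 or 6 strata), and the MMRM's listed terms include neither centre nor sex. That the ANOVA names neither is true but is weaker evidence.

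The statistical consequence is conditional and modest. Under sex-by-centre stratification the standard error is overstated by about 2.6% at an assumed R² of 5% and by about 4 to 5% at 10%. In the simulated ANOVA, adjustment gained about 1 and 4 points of power. The overstatement is smaller if only site is stratified and nil if the strata are not prognostic. Type I error is not inflated. The sizes rest on the assumed R² and an assumed SD of 5.0, and the simulation covers the ANOVA. For the MMRM, the relevant R² is what the strata explain beyond baseline MADRS.

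**What to change.** 1. State one set of strata in Sections B and I, using one term for centre or site. Sex and centre, as in Section B, is the natural choice; blocks of 4 or 8 remain workable with about 18 patients per stratum.
2. Check the specification of the web randomisation system against that wording.
3. Add centre and sex as fixed effects to the primary ANOVA on change scores and to the MMRM.

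The cost is a wording change, one check, and about 6 degrees of freedom (5 for centre, 1 for sex). With 20% dropout, about 173 patients remain (0.8 × 216), so the loss is trivial: at R² of 0% the simulated model SE rose only from 1.077 to 1.082 and power stayed at 81%. The sample size does not change.
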